7.6. SUBJECT COMPLETION/WITHDRAWAL

7.6.1. Subject Completion

Subjects are considered to have completed the study when all study procedures have been completed as designated by the protocol. Completion should be noted on the Screening and Enrollment Log (or equivalent).

7.6.2. Subject Discontinuation

When an individual who has signed the ICD is not included in the study or discontinues/is discontinued prior to completing the study, the reason is to be documented on the Screening and Enrollment Log (or equivalent) and in the final study report. Reasons for subject discontinuation may include:

- Screen Failure (i.e. fails to meet inclusion/exclusion criteria or chooses not to participate)
- Participant is determined to be ineligible after enrollment
- Subject's choice to withdraw
- Investigator terminated (e.g. noncompliance, etc.)
- AE/SAE (must be reported in accordance with the reporting requirements defined in the AE/SAE section "Adverse Event Reporting").
- Lost to follow-up
- Protocol Violation
- Lack of efficacy
- Study terminated by sponsor
- Death
- Pregnancy
- Other

Subjects may withdraw from the trial at any time at their request, or they may be withdrawn at any time at the discretion of the Sponsor, PI, or designee for safety, behavioral, or administrative reasons. If a subject does not return for a scheduled visit, at least 3 documented attempts will be made to contact the subject in order to establish the reason for withdrawal, and the outcome will be documented. The PI or designee should inquire about the reason for withdrawal, request that the subject return for a final visit, if applicable, and follow-up with the subject regarding any unresolved AEs.

When a subject withdraws from the trial and also withdraws consent for disclosure of future information, no further evaluations should be performed, and no additional data should be collected. The PI and staff may retain and continue to use any data collected before such withdrawal of consent.

Additional subjects may be enrolled in the study to compensate for early subject withdrawal.

8. STATISTICAL ANALYSIS METHODS

The analyses will be based on the Intent-to-Treat (ITT) principle, i.e., all subjects who received laser-induced wounds and started the study treatments will be included in the analysis.

Different Adhesive Bandages Protocol Number: CCSTOH001689

Version & Date: Amendment 3: Final Version 4.0, 28 Aug 2019

8.1. SAMPLE SIZE DETERMINATION

As this is a proof-of-principle study to estimate the effect size, and no prior data are available on these endpoints from previously conducted studies of similar study design on these prototypes, a sample size of 40 with a target completion of at least 30 subjects should provide a reliable estimation of the effect size.

8.2. DATA ANALYSIS

The Biostatistics Group at the Sponsor will be responsible for the statistical analysis of the primary and secondary endpoints. Summary statistics will be provided at each time point for the primary and secondary efficacy and safety assessments. For continuous variables, descriptive summaries will include number of subjects, mean, standard deviation, median, minimum and maximum values. Distributions of categorical variables will be summarized by presenting the number and percent of subjects in each response category.

8.3. ENDPOINTS

8.3.1. Primary Endpoints

The primary endpoint of the study will be "Time to Complete Healing" defined as the time (in days) elapsed from the time of wound creation to 12 PM of the day on which the composite healing score (calculated from the clinical grading of wound healing parameters, as defined below) first meets the complete healing criterion of being at least a score of 8. If a composite healing score does not meet the complete healing criterion by Day 16, the time to complete healing will be censored at the last day on which the composite healing score is available.

The composite healing score will be calculated from the clinical grading of wound healing parameters as follows:

Composite Healing Score = [general wound appearance score + smoothness score + epithelial confluence score] – [erythema score + edema score + crusting/scabbing score]

The composite healing score on a 25-point scale (-12 thru +12) is indicative of the extent of wound healing and will be calculated for each wound site at each evaluation day.

Time to complete healing will be analyzed using a survival analysis method. The survival function (cumulative percentage of wounds healed at each time point) will be estimated by the Kaplan-Meier method for each treatment separately. The median time to complete healing will be derived from the estimated survival functions and be compared using the bootstrap re-sampling method.

8.3.2. Secondary Endpoints

The secondary endpoints for this study are the change from baseline* to each applicable time point (see Table 2) for the following parameters:

- Change from baseline* to each applicable time point (see Table 2) for the following parameters:
 - o TEWL measurements
 - Clinical Grading of Wound Healing Erythema

Protocol Number: CCSTOH001689

Version & Date: Amendment 3: Final Version 4.0, 28 Aug 2019

- Clinical Grading of Wound Healing Edema
- Subject self-assessment questions 1, 3, and 5.
- Composite Scar Score calculated as the sum of the individual parameters on the Manchester Scar Scale (Color, Finish, Contour, Distortion and Texture). Composite Scare Scores range from 5 to 18, with 5 representing clinically best scars and 18 representing clinically worst scars.
- Subject self-assessment questions 2 and 4 at each applicable time point.

*Baseline is considered the Day 0 Pre-Wound time point for all endpoints except the subject self-assessment questions. For the subject self-assessment questions, baseline is considered the Day 0 Post-Wound time point.

TEWL measurements, erythema, edema, the composite scar score, and self-assessment questions 1, 3, and 5 will be analyzed within-treatment and between-treatment. The within-treatment comparison will be performed at each post-baseline time point by comparing the post-baseline scores with the baseline score within each treatment using the paired t-test. The between-treatment comparison will be performed by comparing the change from baseline between treatments using a mixed effect analysis of covariance (ANCOVA) model. The ANCOVA model will include the treatment as the factor and the baseline value as the covariate. The model will include subject as a random effect to incorporate the within-subject correlation.

Self-assessment questions 2 and 4 will be summarized by frequency distribution for each treatment at each collection time point.

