6.6. RANDOMIZATION/IP ALLOCATION AND BLINDING

Upon signing the ICD, each subject will be sequentially issued an eight-digit subject ID. The first four digits will be the center ID, 1001, and the next four digits will be a unique subject identifier assigned in ascending numerical order beginning with 1001 (i.e. subject ID 10011001, 10011002, 10011003, etc.).

Different Adhesive Bandages Protocol Number: CCSTOH001689

Version & Date: Amendment 3: Final Version 4.0, 28 Aug 2019

Qualified subjects will be assigned a randomization number sequentially from the randomization list at the Baseline visit (Visit 2). Once a randomization number has been assigned to a subject, it cannot be reassigned to another subject.

Randomization of the study treatments to the eight wound sites (see section 7.2.3.3; one study treatment per wound site) will be based on a randomization scheme devised by the Biostatistics Group at the Sponsor using assigned treatment codes (A through H).

Due to the nature of the IPs and the study design, it is not feasible to fully blind the IPs or to conceal the treatment assignments from study subjects or from all study personnel (i.e. those involved in applying/removing the IPs, IP accountability, or assessing subject compliance). Staff responsible for IP accountability and IP application/removal (hereafter "unblinded staff") will have access to the randomization schedule in order to accurately administer the study treatments. The unblinded staff will not complete any subject evaluations other than the interview for compliance/AEs.

The PI and staff conducting evaluations other than the interview for compliance/AEs (hereafter "blinded staff") will not have access to the randomization schedule, and the IPs will be kept separate from the blinded staff. Subjects will be instructed not to disclose information about their assigned study treatments to blinded staff, or to discuss any other information that may reveal the treatment assignment.

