7.2.4.1. Benzocaine/Lidocaine/Tetracaine Cream Application

Anhydrous numbing Benzocaine/Lidocaine/Tetracaine (BLT) cream (20%/8%/8%) will be topically applied as a thick layer (approximately 2 cm x 2 cm area) at each test site, approximately 30 minutes prior to wounding procedure.

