7.2.5.2. IP Application

After completion of the clinical grading and instrumental evaluations, IPs will be applied to the randomly assigned test sites, as described in section 6. The untreated test site will remain uncovered.

Subjects will be reminded of the study instructions (Appendix III).

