7.2.5.3. Self-Assessment Questionnaire

[figure not shown]
Subjects will be asked to remotely complete a self-assessment questionnaire (see Appendix VI) approximately 3-4 hours after the BLT cream application, when numbness is gone.

Version & Date: Amendment 3: Final Version 4.0, 28 Aug 2019

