7.2.6. Visits 3-16 (Days 1-14)

The following procedures will be completed:

• Subjects will be interviewed for any changes in their medical history or concomitant medications since the last visit. Any AEs will be recorded.

- Subjects will acclimate as described in section 7.2.3.4.
- After the acclimation period, the following evaluations will be conducted for each test site:
 - o Clinical Grading of Wound Healing Parameters, as described in section 7.2.3.5.
 - o Instrumental measurements, as described in section 7.2.3.7.
- The designated IP will be applied to each test site per the randomization schedule.
- At Visits 3-6: Subjects will complete the self-assessment questionnaire at the study site (Appendix VI) after the IP application.

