Appendix VI. Subject Self-Assessment Questionnaire (Day 0 through Day 4)

<Additional Day 0 Instructions: Please complete this questionnaire as soon as the numbness is gone (this will be around 3-4 hours after the numbing cream was applied).>

Please answer the following questions for each wound on your forearms. Focus on each wound itself (not the surrounding skin that might also be covered by a bandage). The wound sites are numbered as shown in Picture 1. Some of the questions will use the scale in Picture 2.

Picture 1. Wound Site Numbering

Picture 2. Scale for Answering Questions 1, 3, and 5

Note: If you cannot provide an answer for a specific wound site because you cannot distinguish the pain/itch sensation from neighboring wounds, choose "Cannot Distinguish" or enter an X.

	Wound Site (see Picture 1 above)							
Question	1	2	3	4	5	6	7	8
1) With your arm resting by your side, how painful/sore is each wound site? Use the scale in Picture 2.								
2) Is the pain (described in #1) brief (B), periodic (P), or constant (C)?								
3) With your arm in normal motion, how painful/sore is each wound site? Use the scale in Picture 2.								
4) Is the pain (described in #3) brief (B), periodic (P), or constant (C)?								
5) How itchy is each wound site? Use the scale in Picture 2.								

⁸ Buckenmaier CC, Galloway KT, Polomano RC, McDuffie M, Kwon N, Gallagher RM. Preliminary validation of the Defense and Veterans Pain Rating Scale (DVPRS) in a military population. Pain Medicine. 2013 Jan 1;14(1):110-23.

Different Adhesive Bandages Protocol Number: CCSTOH001689

Version & Date: Amendment 3: Final Version 4.0, 28 Aug 2019

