TEWL measurements, erythema, edema, the composite scar score, and self-assessment questions 1, 3, and 5 will be analyzed within-treatment and between-treatment. The within-treatment comparison will be performed at each post-baseline time point by comparing the post-baseline scores with the baseline score within each treatment using the paired t-test. The between-treatment comparison will be performed by comparing the change from baseline between treatments using a mixed effect analysis of covariance (ANCOVA) model. The ANCOVA model will include the treatment as the factor and the baseline value as the covariate. The model will include subject as a random effect to incorporate the within-subject correlation. The adjusted mean of each product from the ANCOVA model will be compared between the IPs and the negative control, between the IPs and the IP - █ between the IPs (except the IP - █ and the IP – Benchmark Control 1, and between the IPs (except the IP - █ and the IP – Benchmark Control 1) and the IP – Benchmark Control 2).

The mixed effect analysis of covariance model can be performed by the following SAS codes

PROC MIXED DATA = <dataset>;

CLASS subjid treatment;

```
MODEL chg = treatment baseline/solution ddfm = contain;  
RANDOM subjid ;  
LSMEANS treatment/diff cl;  
ESTIMATE "IP - █ vs. Negative Control" treatment 1 0 0 0 0 0 0 -1 /cl;  
ESTIMATE "Product #1 vs. Negative Control" treatment 0 0 0 1 0 0 0 -1 /cl;  
...  
RUN;
```

Note:

Self-assessment questions 2 and 4 will be summarized by frequency distribution for each treatment at each collection time point.

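### The baseline for the pain and itch questions is scored after the bandages are on, so the planned ANCOVA removes part of any early treatment effect

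*Protocol*

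**What the plan says.** Protocol 8.3.2 and SAP 4.2.2 make change from baseline in questions 1, 3 and 5 secondary endpoints. The other change-from-baseline endpoints use the pre-wound assessment. For the questionnaire, "For the subject self-assessment questions, baseline is considered the Day 0 Post-Wound time point".

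The Day 0 order is set out in Protocol 7.2.4 and 7.2.5:

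- Numbing cream goes on "approximately 30 minutes prior to wounding procedure".
- The wounds are made, then graded, and TEWL is measured.
- "After completion of the clinical grading and instrumental evaluations, IPs will be applied to the randomly assigned test sites". Protocol 6.5.2 confines application to the study site.
- The questionnaire is completed remotely, "approximately 3-4 hours after the BLT cream application, when numbness is gone".

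Table 2 schedules no earlier questionnaire. For Visits 3 to 6 (Days 1 to 4), Protocol 7.2.6 says: "Subjects will complete the self-assessment questionnaire at the study site (Appendix VI) after the IP application".

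For the between-treatment analysis of change in these questions, SAP 6.3 says: "The ANCOVA model will include the treatment as the factor and the baseline value as the covariate". Subject is a random effect. Within each treatment, each later day is compared with baseline by paired t-test. SAP 4.5, which lists the endpoints that take a baseline covariate, does not name questions 1, 3 and 5.

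**The concern.** Adjusting for a baseline, or subtracting it, is safe when treatment cannot have influenced it. Here it can: the Day 0 answers are given with seven wounds bandaged and one bare, and the form itself expects this ("Focus on each wound itself (not the surrounding skin that might also be covered by a bandage"). Day 0 is the same kind of measurement as Days 1 to 4.

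Any effect of a bandage on pain or itch in the first hours is therefore partly removed from every later comparison. A product that helps early and keeps helping looks weaker than it is. A product whose early benefit fades can look harmful later. An early effect in the opposite direction exaggerates the later result. Tables 14.2.6 to 14.2.8 report the only planned between-treatment tests of these questions, and they could not be read as the treatment difference on a given day.

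**Working it through.** The plan gives no effect size, SD or slope for these questions, so there is no figure of its own to reproduce.

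**1. Timing.** The questionnaire falls 3 to 4 h after the cream, and wounding about 0.5 h after it. That places the answers about 2.5 to 3.5 h after wounding begins (3 − 0.5 and 4 − 0.5). Bandage wear is shorter than that by the time taken for wounding, grading, TEWL and application. The exact interval is not stated.

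**2. Algebra.** The SAP code regresses change (Yt − Y0) on treatment and Y0, with coefficient g on Y0. This is the same as regressing Yt on treatment and Y0 with slope b = 1 + g. With complete data and all eight treatments in every subject, the adjusted contrast is exactly

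(difference in mean Yt) − b × (difference in mean Y0),

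which estimates dt − b·d0. Unadjusted change would estimate dt − d0. It would apply between treatments only if the omission in SAP 4.5 overrides SAP 6.3.

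**3. Check of the identity.** In one simulated data set fitted with the SAP model, g = −0.1558, so b = 0.8442. Then −1.6338 − 0.8442 × (−1.7226) = −0.1796, and the fitted contrast was −0.1796.

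**4. Size under assumed inputs.** The response scale is not visible, so all inputs are assumptions: 30 subjects × 8 wounds, wound-level SD 1, subject SD 1.5, subject-level correlation 0.7, and wound-level correlation 0.3, 0.5 or 0.7. The random-subject ANCOVA then gives b of about 0.37, 0.53 and 0.70. There were 1,000 simulated trials per case, comparing one bandage with the uncovered wound. Negative means less pain.

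| d0 | dt | Planned ANCOVA (correlation 0.3 / 0.5 / 0.7) | Observed-score model |
|---|---|---|---|
| 0 | −1 | −1.00 / −1.00 / −1.00 | unbiased |
| −1 | −1 | −0.63 / −0.46 / −0.30; power 71 / 51 / 35% | −1.00; power 97–98% |
| −1 | −0.5 | −0.13 / +0.03 / +0.20 | −0.50 |
| +0.5 | −0.5 | −0.68 / −0.76 / −0.85 | −0.50 |
| −1 | 0 | +0.35 / +0.54 / +0.70; falsely worse in 29 / 64 / 95% | 0.00; falsely worse in 2–3% |

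Each ANCOVA mean is within about 0.02 of dt − b·d0. In the second row, for example, −1 + 0.37 = −0.63. With d0 = dt = 0, both models rejected in about 4–6% of trials.

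**5. Precision given up by dropping the covariate.** With wound-level SD 1, the observed-score contrast has variance 2/30 = 0.067. In a purely within-subject version of the model, b is about the wound-level correlation r, and the covariate saves variance of about 2r²/30 but adds squared bias r²·d0². The two are equal at |d0| = √(2/30) ≈ 0.26 SD. At d0 = 0 and dt = −0.5, power is about 53 / 61 / 77% with the covariate and about 49% without.

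**The case against.** The strongest defence is that the definition is disclosed. Both documents name this baseline, and the endpoint is change from it, so the contrast is shifted only against a target that the plan does not claim. A useful pain score before bandaging is also hard to obtain at that visit, because the skin is numb. Both facts are right, but neither rescues the contrast. Numbness explains the timing without making the score pre-treatment, and the ANCOVA does not estimate pure change (dt − d0) either. It estimates a mixture whose weight b is learned from the data.

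Second, Protocol 8.2 and SAP 6 promise summary statistics at each time point, and Listing 16.2.6.4 gives individual answers. A reader may therefore be able to see the Day 0 difference. That helps interpretation but does not repair the test.

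Third, the larger distortions rest on an early effect of 0.5 to 1 SD, which nothing in the documents supports. With d0 = −0.2 and dt = 0, the ANCOVA rejects in only about 6 / 8 / 12% of trials. Below roughly a quarter of an SD, its mean squared error is the smaller (step 5). This stands: the size is unknown, and the remedy has a price when early effects are small. It is the usual price of not conditioning on something treatment may have changed.

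Finally, these are three secondary outcomes in an exploratory study with unadjusted tests. That limits the weight of the point. But Protocol 8.1 gives estimating the effect size as the purpose, so a shifted estimate still matters.

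**Conclusion.** The plan is wrong as written on this point and should be corrected. The order of procedures makes the Day 0 questionnaire an on-treatment score, and the planned contrast is dt − b·d0. That follows from the documents and algebra and needs no assumed figures.

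The size does rest on assumptions. The bias is zero if bandages do nothing to pain or itch in the first hours. It attenuates the later effect when both effects run the same way, reverses its sign only when b·d0 exceeds dt in size, and exaggerates it when they run in opposite directions. Only the part of d0 caused by treatment is a bias; adjusting for chance imbalance would be proper. If SAP 4.5 were to govern, the shift would be the whole of d0.

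The within-treatment paired t-tests start from the same on-treatment score. The primary endpoint, and the secondary endpoints that use the pre-wound baseline, are not affected.

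**What to change.** In Protocol 8.3.2 and SAP 4.2.2, 4.5 and 6.3, make the Day 0 questionnaire an outcome. Compare observed scores of questions 1, 3 and 5 between treatments at each of Days 0, 1, 2, 3 and 4 with the same mixed model (treatment fixed, subject random), without a change score or Day 0 covariate. Treatments are randomised to sites within each subject (Protocol 6.6), so the comparison is unbiased without a baseline. It also reports the early effect, which the present plan does not test.

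Keep change from Day 0 and its paired t-test only to describe the time course, labelled as change since the first on-treatment score. State in SAP 4.5 that these questions take no baseline covariate, so that 4.5 and 6.3 agree.

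A lighter remedy would relabel the estimand, reconcile 4.5 with 6.3 and add the observed-score comparison as a sensitivity analysis. That would disclose the problem but leave the mixed contrast as the main test.

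The cost is a protocol amendment with Sponsor and IRB/IEC approval (Protocol 10.1), matching SAP edits, a small change to the model code and new titles for Tables 14.2.6 to 14.2.8. No new data, visits or subjects are needed. The statistical cost is the loss of precision in step 5 if early effects are absent or small.

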7.2.3.2. Randomization

A unique randomization number will be assigned to each subject as described in section 6.6.

Version & Date: Amendment 3: Final Version 4.0, 28 Aug 2019

7.2.3.3. Identification of Test Sites and Application of Temporary (Semi-Permanent) Dot-Tattoos and Test Site Labels

Eight test sites (i.e. wound sites) will be identified on the volar forearms, four on each forearm, as shown in Figure 6.

[figure not shown]

Figure 6. Wound Site Placement

Going from the elbow to the wrist, the test sites on the right volar forearm will be designated test sites 1, 2, 3, and 4, and those on the left volar forearm will be designated test sites 5, 6, 7, and 8. The test sites will be spaced such that the wounds (see section 7.2.4.3.) will be created at least 4.0 cm apart so that the IPs will not overlap when applied.

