7.2.5. Visit 2/Baseline (Day 0) – Post-Wound Time Point

7.2.5.1. Clinical/Instrumental Evaluations

After wound creation, the following evaluations will be completed on each test site in the order below:

- Clinical grading of wound healing parameters, as described in section 7.2.3.5.
- •
- •
- TEWL Measurements, as described in section 7.2.3.7.3

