7.5.3. TEWL Measurements (Tewameter TM300 or TM330T; Courage + Khazaka, Köln, Germany)

TEWL, the passive transfer of water through the stratum corneum, will be measured for each wound site at Visit 2 Baseline/Pre-Wound time point, Visit 2 Post-Wound time point, and Visits 3-16 using the Tewameter TM300 or TM330T (Courage + Khazaka electronic GmbH, Köln, Germany). The same instrument (Tewameter TM300 or TM330T) that is used at Day 0 for one subject will be used for all subsequent measurements.

The measurement of water evaporation is based on the diffusion principle in an open chamber and the density gradient is measured indirectly by two pairs of sensors located inside the hollow cylindrical probe. Data are analyzed by a microprocessor and reported in $g/m^2/h$. A decrease in TEWL values reflects a decrease in the rate of water loss of the skin.

Duplicate 30-second measurements will be taken for each wound site; if the TEWL reading is not stable within 30 seconds, the measurement should be expanded to 60 seconds. A sterile metal adaptor ring (C+K Catalog # Z00812) will be mounted on the measuring head of the probe. The metal adaptor ring will be cleaned with an ethanol wipe between wound sites on the same subject and allowed to completely air dry before each reading. The metal adaptor rings will be thoroughly cleaned and autoclaved between subjects.

Different Adhesive Bandages Protocol Number: CCSTOH001689

Version & Date: Amendment 3: Final Version 4.0, 28 Aug 2019

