4.2.2 Secondary Efficacy Endpoint

The secondary endpoints for this study are the change from baseline* to each applicable time point (see Table 2) for the following parameters:

- Change from baseline* to each applicable time point (see Table 2) for the following parameters:
 - TEWL measurements
 - Clinical Grading of Wound Healing – Erythema
 - Clinical Grading of Wound Healing – Edema
 - Subject self-assessment questions 1, 3, and 5.
 - Composite Scar Score – calculated as the sum of the individual parameters on the Manchester Scar Scale (Color, Finish, Contour, Distortion and Texture). Composite Scar Scores range from 5 to 18, with 5 representing clinically best scars and 18 representing clinically worst scars.
- Subject self-assessment questions 2 and 4 at each applicable time point.

*Baseline is considered the Day 0 Pre-Wound time point for all endpoints except the subject self-assessment questions. For the subject self-assessment questions, baseline is considered the Day 0 Post-Wound time point.

[REDACTED]

[REDACTED]

[REDACTED]

[REDACTED]

[REDACTED]

[REDACTED]

[REDACTED]

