4.5 Covariates

For the analyses of Change from Baseline in TEWL measurements, erythema, edema, the composite scar score, corresponding baseline value will be included in the models as covariate.

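### The secondary between-treatment ANCOVA omits two pre-treatment variables the trial already records, the Day 0 Post-Wound value and the wound site: a cheap improvement, not an error

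*Protocol*

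**What the plan says.** Protocol 8.3.2 sets the between-treatment model for TEWL, erythema, edema, the composite scar score and self-assessment questions 1, 3 and 5: "The ANCOVA model will include the treatment as the factor and the baseline value as the covariate". Subject enters as a random effect. SAP 6.3 repeats this, and its SAS code has only subject and treatment as class variables and only treatment and baseline in the MODEL statement. SAP 4.5, which names TEWL, erythema, edema and the scar score, says the "corresponding baseline value will be included in the models as covariate". SAP 4.2.2 defines that baseline: "Baseline is considered the Day 0 Pre-Wound time point for all endpoints except the subject self-assessment questions".

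Two other variables exist before any bandage is applied.

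- **Day 0 Post-Wound value.** Protocol 7.2.5.1: "After wound creation, the following evaluations will be completed on each test site in the order below". The list includes clinical grading (hence erythema and edema) and TEWL. Protocol 7.5.3 gives the TEWL time points as "Visit 2 Baseline/Pre-Wound time point, Visit 2 Post-Wound time point, and Visits 3-16". Protocol 7.2.5.2 fixes the order: "After completion of the clinical grading and instrumental evaluations, IPs will be applied to the randomly assigned test sites".
- **Wound site.** Protocol 6.6 describes "Randomization of the study treatments to the eight wound sites", one treatment per site. Protocol 7.2.3.3 numbers the sites: "Going from the elbow to the wrist, the test sites on the right volar forearm will be designated" 1 to 4, and those on the left 5 to 8.

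Neither variable is in the visible model text, covariate section or code.

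**The concern.** For erythema and edema the planned covariate is a grade of intact skin before lasering. It is expected, though not documented, to be near 0 at most sites, so it can adjust for little. The measurement that records how much injury each site received is not used. Site is the unit to which treatment is allocated within a subject, so any trend along the forearm stays in the residual.

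What is at stake is interval width. Protocol 8.1 gives effect-size estimation as the purpose of the study, so precision matters even though SAP 6.2 declares the tests exploratory.

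A smaller point of wording: the secondary endpoints are analysed at each applicable time point in Table 2, and Table 2 marks Day 0 Post-Wound for TEWL and grading. The text allows, but does not require, that time point to be read as an outcome visit.

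**Working it through.** **The plan's own figure.** There is none to reproduce. Protocol 8.1 gives 40 subjects with at least 30 completing, and no SD, effect size or power.

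**Eligibility as covariates.** The Post-Wound value precedes the bandage for TEWL, erythema and edema. It does not exist for the scar score, which is scored only at Day 0 Pre-Wound and Day 28. For questions 1, 3 and 5 the Day 0 answer is given remotely 3 to 4 hours after the numbing cream (Protocol 7.2.5.3), after the visit at which the bandages are applied, so it is not a pre-treatment value. Site is available for every outcome.

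**Degrees of freedom.** Planned residual df = 8N − N − 7 − 1.

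- N = 30: 240 − 30 − 7 − 1 = 202. Adding site (7) and Post-Wound (1) leaves 194.
- N = 40: 320 − 40 − 7 − 1 = 272, falling to 264.

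**Approximate width ratio** (adjusted / planned) when the planned covariate explains nothing:

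ratio ≈ √[(1 − s)(1 − r²)] × √(df planned / df adjusted)

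Here r is the within-subject correlation of the Post-Wound value with the outcome, and s is the share of within-subject variance due to site. Both are assumptions. With N = 30 the last factor is √(202/194) = 1.020.

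- r = 0, s = 0: 1.020
- r = 0.2, s = 0: √0.96 × 1.020 = 1.00
- r = 0.2, s = 10%: √(0.90 × 0.96) × 1.020 ≈ 0.95
- r = 0.5, s = 0: √0.75 × 1.020 = 0.88

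**Simulation** (1500 trials per cell, 8 sites per subject, random permutation of treatments, linear elbow-to-wrist effect, planned covariate uninformative). Ratio of mean 95% half-widths:

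| Terms added | r | s | N = 30 | N = 40 |
|---|---|---|---|---|
| both | 0 | 0 | 1.021 | 1.015 |
| both | 0.2 | 0 | 1.001 | 0.995 |
| both | 0.2 | 5% | 0.970 | 0.967 |
| both | 0.2 | 10% | 0.942 | 0.937 |
| both | 0.5 | 0 | 0.883 | 0.879 |
| site only | – | 0 | 1.018 | 1.013 |
| site only | – | 5% | 0.988 | 0.984 |
| site only | – | 10% | 0.959 | 0.955 |

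**Informative planned covariate.** The baseline for TEWL and for questions 1, 3 and 5 is itself specific to the site and may already carry the site effect. Site-only ratio, N = 30, s = 10%:

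- Baseline correlation 0.5, same site effect in the baseline: 1.00 (about 1.01 at correlation 0.7).
- Correlated baseline with no site effect in it: 0.94.

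**Grading floor.** With half-point grades clipped to 0–4 and about 1/50/80/91% of sites graded 0, the N = 30 ratios are 0.903/0.932/0.969/0.990 at r = 0.5, s = 0, and 0.948/0.965/0.988/1.003 at r = 0.2, s = 10%.

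**Missing Post-Wound values.** SAP 5 rules out imputation, so such a site leaves the adjusted model at every visit. With 2/5/10% of sites missing at r = 0.2, s = 10%, the ratio is 0.956/0.976/1.006 (N = 30). With neither term informative and 10% missing it is 1.089.

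**Type I error of the planned model.** Under random permutation it is 4.4 to 5.5% over 32 cells, which is nominal. If allocation is balanced over sites (Latin square) it is about 4% at s = 10% and about 2.5 to 3% at s = 20%. At s = 5% separate runs gave 4.1 to 5.2%, not clearly different from 5%.

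**The case against.** The strongest reply is that nothing here is broken. Treatment, baseline and random subject form a valid model for this design, the tests are exploratory and unadjusted, and the benefit rests on two quantities the documents do not give. The one relevant fact, that the laser specialist is to create uniform wounds (Protocol 7.2.4.3), points to a small gain. All of this stands, and it is why the point is an improvement only.

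A second reply is that another model adds output. On the visible wording SAP 6.3 lists 7 + 6 + 5 + 4 = 22 contrasts. If every scheduled visit is analysed there are 14 (TEWL) + 16 + 16 (erythema, edema) + 1 (scar) + 12 (three questions on four days) = 59 outcome-visits, or 59 × 22 = 1,298 unadjusted contrasts. A second model doubles that. This also stands, so the SAP must say which model governs.

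A third is that parts of the SAP are redacted and the note after the SAS code is blank. A supportive model could be hidden there.

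Stronger readings that a reader might infer are not supported:

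- *The planned contrasts are biased because baseline is intact skin.* For TEWL, erythema, edema and the scar score they are not, provided wounding does not depend on allocation. No such assurance is given for questions 1, 3 and 5, because their baseline follows bandage application.
- *The planned tests are conservative.* That requires an allocation balanced over sites, and Protocol 6.6 does not describe the scheme.
- *A site term will narrow every interval.* For TEWL and questions 1, 3 and 5 the baseline may already absorb the site effect.

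**Conclusion.** The point holds as a low-cost precision improvement to exploratory secondary analyses. It is not an error, and time to complete healing is untouched.

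Its size depends on assumed r and s. For erythema and edema, where an uninformative planned covariate is plausible, adding both terms gives intervals from about 2% wider to about 12% narrower over the complete-data cases tabulated. The gain disappears close to the grading floor, if the wounds are as uniform as intended, or with about 10% missing Post-Wound values at r = 0.2 and a 10% site share. For TEWL and questions 1, 3 and 5, at a 10% site share, the site-only ratio runs from about 0.94 to about 1.00, and up to 1.02 if site has no effect. Conservative type I error is conditional on a balanced allocation that the documents do not describe.

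**What to change.** In SAP 4.5 and 6.3, before unblinding, pre-specify for each ANCOVA outcome one model that governs the between-treatment contrasts.

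- Add site as an 8-level fixed effect for every outcome.
- For TEWL, erythema and edema only, add the Day 0 Post-Wound value at that site as a second covariate: `CLASS subjid treatment site; MODEL chg = treatment baseline postwound site`.
- Keep change from Pre-Wound as the outcome for those three, keep the planned baseline covariate, and keep the paired t-tests.
- Report the planned model as a stated sensitivity analysis for all outcomes, whether or not Post-Wound values are missing.
- State that Day 0 Post-Wound is not an outcome visit for between-treatment contrasts.

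The cost is 8 residual df (7 where only site is added), intervals up to about 2% wider with complete data if the terms are uninformative, loss of sites with a missing Post-Wound value, and a second set of unadjusted exploratory contrasts. The data are already captured, so the work is SAP wording and a few lines of code. An amendment needs Sponsor and IRB/IEC approval (Protocol 10.1) and is not warranted for this point alone. The SAP can record the difference from Protocol 8.3.2.
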